12.3.1 Consent and Other Informational Documents Provided to Subjects

The subject/LAR must be given a copy of the signed informed consent and the original maintained in the designated location at the site.

12.3.2 Consent Procedures and Documentation

It is the Investigator or designee's responsibility to obtain written informed consent from the subject/LAR after adequate explanation of the aims, methods, anticipated benefits, and potential hazards of the study. The LAR must be given ample time to decide about study participation and opportunity to inquire about details of the study. The IRB/EC-approved consent form must be personally signed and dated by the LAR with subject assent, if possible, and by the person who conducted the informed-consent discussion. The Investigator or appropriate site personnel must document the details of obtaining informed consent in the subject's study documents.

The subject's caregiver must also indicate their understanding of the study and their role as a caregiver to the subject during the study. The subject's caregiver must provide written consent prior to any study procedures being performed indicating their agreement to participate in the study in the caregiver role.

Participation in the caregiver interview is optional. Informed consent must be obtained by the Investigator (or designee), as appropriate, prior to the interviewer contacting the caregiver and conducting the optional caregiver interview.

Where applicable and permitted, informed consent forms may be administered remotely in accordance with ICH E6 and applicable regulations.

Records related to a study subject's participation will be maintained and processed according to local laws, and where applicable, the European Union General Data Protection Regulation (EU GDPR). The consent and study information documentation will include statements describing local and regional requirements concerning data privacy, and who to contact for questions.

13 PUBLICATION PLAN

All publication rights are delineated in the Clinical Study Agreement and/or other separate agreements with the Investigator and/or Institution, as applicable.

14 CONFLICT OF INTEREST POLICY

14.1 Finance, Insurance, and Indemnity

Arrangements for finance, insurance, and indemnity are delineated in the Clinical Study Agreement and/or other separate agreements with the Investigator and/or Institution, as applicable.

## ABBREVIATIONS

AE	adverse event
ATC	Anatomical/Therapeutic/Chemical
BMI	body mass index
CI	confidence intervals
CGI-I	Clinical Global Impression – Improvement
CGI-S	Clinical Global Impression – Severity
COVID-19	coronavirus disease 2019
DB	double-blind
DSMB	Data and Safety Monitoring Board
eCRF	electronic case report form
ECG	Electrocardiogram
EDC	electronic data capture
FDA	Food and Drug Administration
GJ	Gastrojejunal
GSD	Guidance for Site Documentation and Data Management Querying of Data Impacted by COVID-19
ICND	Impact of Childhood Neurologic Disability Scale
MedDRA	Medical Dictionary for Regulatory Activities
NDA	new drug application
PCI	potentially clinically important
PHE	public health emergency
QTcB	QT Interval Corrected for Heart Rate using Bazett's Formula
QTcF	QT Interval Corrected for Heart Rate using Fridericia's Formula
RSBQ	Rett Syndrome Behaviour Questionnaire
RTT	Rett Syndrome
RTT-AMB	Rett Syndrome Clinician Rating of Ambulation and Gross Motor Skills
RTT-CBI	Rett Syndrome Caregiver Burden Inventory
RTT-COMC	Rett Syndrome Clinician Rating of Ability to Communicate Choices
RTT-CSS	Rett Syndrome Clinical Severity Scale

RTT-DSC	RTT Domain Specific Visual Analog Scale
RTT-HF	Rett Syndrome Clinician Rating of Hand Function
RTT-VCOM	Rett Syndrome Clinician Rating of Verbal Communication
SAE	serious adverse event
SAP	statistical analysis plan
SD	standard deviation
SE	standard error
SOC	system organ class
TEAE	treatment-emergent adverse event

## 1. INTRODUCTION

This statistical analysis plan (SAP) provides a technical and detailed elaboration of the statistical analyses of efficacy and safety data for Study ACP-2566-005. This plan should be read in conjunction with the study protocol and the electronic case report forms (eCRFs).

The SAP version 1.0 is based on protocol version 1.0, dated 11 September 2020. The SAP version 2.0 is based on protocol Amendment 1, dated 19 December 2022. Main changes include:

- added summary for number of caregivers consented and participated for optional exit interview
- added summary for number of subjects who took commercially marketed trofinetide within 30 days after study completion
- updated definition for treatment-emergent adverse events with Day 1 onset.

Note that for the caregiver optional exit interviews, following the analysis of the qualitative data, a summary report that describes the objectives, methods, participants, and results of the qualitative interviews will be prepared and reported separately from the clinical study report.

## 2. OBJECTIVES

### 2.1 Primary Objective

The primary objective of this study is to investigate the safety and tolerability of continued long-term treatment with oral trofinetide in girls and women with Rett syndrome.

### 2.2 Exploratory Objectives

The exploratory objectives for this study are:

- To investigate the efficacy of long-term treatment with oral trofinetide in girls and women with Rett syndrome
- To investigate the efficacy of long-term treatment with oral trofinetide in girls and women with Rett syndrome on overall ability to communicate
- To investigate the benefit of long-term treatment with oral trofinetide on overall quality of life for girls and women with Rett syndrome
- To investigate the efficacy of long-term treatment with oral trofinetide in girls and women with Rett syndrome on:
  - Hand function
  - Ambulation and other gross motor skills
  - Ability to communicate choices and preferences
  - Ability to communicate verbally
- To investigate the efficacy of long-term treatment with oral trofinetide on a global assessment of the severity of illness in girls and women with Rett syndrome
- To investigate the benefit of long-term treatment with oral trofinetide on the burden on caregivers of girls and women with Rett syndrome
- To investigate the benefit of long-term treatment with oral trofinetide on the impact of the disability on the child's and family's everyday life

### **3. STUDY DESIGN**

#### **3.1 General Study Design**

This is a multi-center, open-label, long-term study of trofinetide to monitor the safety and efficacy of continuing trofinetide therapy. Subjects who complete the preceding open-label study (ACP-2566-004) will be eligible to enroll in the present study.

[figure not shown]
The duration of participation for individual study subjects will be approximately 32 months, or less than 32 months if: 1) trofinetide becomes commercially available for the treatment of Rett syndrome or 2) if development of trofinetide for Rett syndrome is discontinued. The Sponsor may discontinue the study for any reason. Note that not all subjects entering the present study will be treated for 32 months. It is anticipated that the time from which the first subject enters the present study until the predicted time that trofinetide receives marketing authorization and is marketed will be 29 months. Therefore, subjects who enter the present study, for example, 6 months after the first subject enters, will receive treatment with trofinetide for approximately 23 months before the study is terminated based on the anticipated date of commercial availability of trofinetide.

Legally acceptable representatives (LARs)/subjects must be consented prior to the procedures being performed at the end of treatment (EOT) visit of the antecedent study. The EOT visit of the antecedent study will serve as the Baseline visit of the present study. The data gathered at the EOT visit of the antecedent study serves as the baseline data of the present study. The duration of participation for individual study subjects will be up to approximately 32 months with a safety follow-up period of 30 (+4) days. Approximately 28 sites will participate in this study.

The study will have two periods ([Figure 1](#)):

- Treatment period: up to approximately 32 months
- Safety follow-up period: 30 days

**Figure 1 Schematic of Study Design**

The schedule of events and assessments is provided in the appendix ([Section 20.1](#)). As shown in the schedule of events, study visits may be done off-site rather than in the clinic, where appropriate and applicable.

The study completion date is defined as the date the final subject, across all sites, completes their final protocol-defined assessment. An individual subject is considered to have completed the study on the date of her final protocol-defined assessment. Please note that the “final protocol-defined assessment” includes the follow-up visit or contact, whichever is later. A subject will be considered lost to follow-up if they fail to attend a scheduled visit (excluding the safety follow-up telephone call) and the study site is unable to contact the subject or caregiver.

Every reasonable effort should be made to contact the caregiver and will include a minimum of 3 documented telephone calls and, if necessary, a certified letter to the subject’s last known mailing address or local equivalent methods. All contact attempts are to be documented in the source documents.

### **Open-label Treatment Period**

The EOT visit of the antecedent trofinetide study (e.g., ACP-2566-004) serves as the Baseline visit (Visit 1) of the present study. The day the first dose is taken will be considered Day 1 of dosing. Dosing is twice a day, once in the morning and once in the evening.

The subject’s assigned dose for this study will be the final dose from the antecedent study. If the subject’s weight at the Baseline visit of the present study puts them in a new weight category ([Table 1](#)), the Investigator may decide to increase the dose to the dose associated with the new weight category. Similarly, if the subject’s weight after 52 weeks in the present study, or thereafter puts them in a new weight category, the Investigator may decide to increase the dose to the dose associated with the new weight category.

**Table 1 Dosing Schedule Based on Weight at Baseline of the Present Study**

Weight	Dose	Total Daily Dose
12-20 kg	30 mL (6 g) BID	60 mL (12 g)
>20-35 kg	40 mL (8 g) BID	80 mL (16 g)
>35-50 kg	50 mL (10 g) BID	100 mL (20 g)
>50 kg	60 mL (12 g) BID	120 mL (24 g)

BID = twice daily

If the subject cannot tolerate administration of the full assigned dose the Investigator may instruct the caregiver to reduce study drug to a dose as low as 3 g (15 mL) BID. In addition, up to 4 doses (in total, consecutive or non-consecutive) may be held for this reason.

Study drug is administered twice a day, once in the morning and once in the afternoon or evening. There should be at least 8 hours between doses. The study drug may be given with or without food.

In addition to the study drug dispensed at the Baseline visit, additional investigational product will be shipped directly to the subject. Confirmation of delivery to the subject will be made by a visiting nurse. Study drug shipment, return, and accountability will be performed in accordance with the drug distribution plan.

Subjects will have assessments completed at Week 12, Week 52, Week 104, and Week 130. Assessments may be completed in the clinic or off-site, at the discretion of the Principal Investigator.

### **Safety Follow-Up Period (30 [+4] Days)**

A 30 (+4) day safety follow-up telephone or telemedicine contact is to be completed for subjects if they do not begin to take commercially marketed trofinetide within the 30 days after completing the study or if they discontinue prematurely from the study. The contact includes assessment of concomitant medications and treatments and assessment of AEs.

### **3.2 Randomization**

Not Applicable. This is not a randomized study.

### **3.3 Blinding**

Not Applicable. This is an open-label study.

### **3.4 Determination of Sample Size**

The sample size of this open-label study is not determined based on statistical considerations. However, subjects enrolled in the present study are those who have completed the antecedent study, ACP-2566-004, and rolled over to the present study. Since approximately 180 subjects are to be enrolled in the ACP-2566-004 study and it is expected 85% of these subjects will complete Study ACP-2566-004 and rollover to the present study, the number of subjects in the present study will be approximately 153.

### **3.5 Coronavirus Disease 2019**

In March 2020, the emerging coronavirus disease 2019 (COVID-19) pandemic resulted in implementation of urgent safety measures designed to ensure subject safety. Mechanisms to record information on the potential impact of the COVID-19 pandemic on data itself, as well as data collection and integrity, were implemented (as detailed in the appendix of ACP-2566-005's Data Management Plan titled "Guidance for Site Documentation and Data Management Querying of Data Impacted by COVID-19" [GSD] included in eTMF).

Relationship to the public health emergency caused by the COVID-19 pandemic will be assessed for early terminations, protocol deviations, selected medications, and selected adverse events as detailed in the GSD.

#### **4. ANALYSIS SETS**

##### Safety Analysis Set

The Safety Analysis Set consists of all subjects who received at least one dose of study drug in this study.

## 5. DATA HANDLING CONVENTIONS

All data collected in the study will be listed.

### 5.1 General Data Reporting Conventions

Continuous variables will be summarized using the following descriptive statistics: number of subjects, mean, standard error (SE), standard deviation (SD), median, minimum, and maximum. For descriptive summaries of efficacy changes from baseline, the 95% confidence interval (CI), calculated as mean  $\pm$  1.96\*SE, will be presented. Unless specified otherwise, means, medians, and CIs will be presented to one more decimal place than the raw data, and the SDs and SEs will be presented to two more decimal places than the raw data. In general, the maximum number of decimal places is 4 and values will be truncated to 4 decimal places in situations where there are more than 4 decimal places. Wherever possible data will be decimal aligned.

Height, weight and BMI will be presented with a maximum of one decimal place.

Categorical variables will be summarized by the number of subjects and the percentage of subjects in each category; the number of subjects and the percentage of subjects with missing data will be summarized for demographic and baseline characteristics (if applicable). Categories with zero counts will not have zero percentages displayed. For demographic summaries, percentages will be calculated by using the total number of subjects in the given treatment group of the antecedent double-blind (DB) study (ACP-2566-003) as the denominator. Percentages will be presented with one decimal place.

Duration in months will be calculated as ([the number of days / 365.25] \*12).

Clinical laboratory assessment values that are collected with “<” or “>” signs will generally be analyzed as the numerical value without the sign in tables and figures. In listings, these data will be reported as collected with the sign.

For each continuous measure in safety and efficacy analyses, change from baseline results will be presented by treatment group of the antecedent DB study ACP-2566-003 and overall in two ways:

1. Main analysis: using the baseline of this study, as defined in [Section 5.5](#), to report the changes across the timepoints of this open-label Study ACP-2566-005.
2. Exploratory analysis: using the baseline from the antecedent study, ACP-2566-003, to report the changes across the timepoints of this open-label Study ACP-2566-005.

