### **5.2.5 Rett Syndrome Clinician Rating of Hand Function (RTT-HF)**

The RTT-HF is a clinician completed clinical assessment of the subject's ability to use her hands for functional purposes. The assessment is made on an 8-point Likert scale (0-7) with 0 denoting normal functioning and 7 the most severe impairment.

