### **5.2.9 Clinical Global Impression–Severity (CGI-S)**

The CGI-S is a 7-point scale that requires the clinician to rate the severity of the subject's illness at the time of assessment, relative to the clinician's experience with subjects who have the same diagnosis. Considering total clinical experience, a subject is assessed on severity of illness at the time of rating: 1=normal, not at all ill; 2=borderline ill; 3=mildly ill; 4= moderately ill; 5=markedly ill; 6=severely ill; or 7=extremely ill.

Higher CGI-S scores denote more severe illness and less improvement in the illness respectively.

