## **12. EFFICACY ANALYSES**

Unless otherwise specified, all efficacy analyses will be performed using the Safety Analysis Set. No hypothesis testing is planned. Descriptive summaries of all efficacy endpoints will be presented.

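### SAP 5.1 builds every 95% confidence interval with a fixed 1.96 and an SE estimated in the same cell, so for roughly normal changes coverage falls slightly below 95%, by more in small cells

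*SAP*

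**What the plan says.** SAP 5.1 defines the interval in one sentence: "For descriptive summaries of efficacy changes from baseline, the 95% confidence interval (CI), calculated as mean" plus or minus 1.96 times the SE. The same paragraph lists the SE beside the number of subjects, mean and SD as an ordinary descriptive statistic, so it is the sample SE of the cell being summarized. No known or model-based variance is mentioned.

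The interval is repeated across many cells. SAP 5.1 says that "change from baseline results will be presented by treatment group of the antecedent DB study ACP-2566-003 and overall in two ways", using either this study's baseline or the ACP-2566-003 baseline. SAP 5.5 adds the split by analysis visit. Neither document gives a t quantile or a rule for small cells.

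SAP 12.1 lists nine change-from-baseline endpoints. Three are sum scores: RSBQ total, CSBS-DP-IT Social and RTT-CBI total. Six are single ratings: four RTT clinician ratings, of which RTT-HF is typical ("The assessment is made on an 8-point Likert scale (0-7) with 0 denoting normal functioning"), CGI-S ("The CGI-S is a 7-point scale that requires the clinician to rate the severity"), and the ICND quality-of-life rating from 1 to 6.

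SAP 12 sets the role of these summaries: "No hypothesis testing is planned. Descriptive summaries of all efficacy endpoints will be presented".

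**The concern.** For normal data, the multiplier 1.96 gives 95% coverage only when the standard error is known. When it is estimated from the same n changes, the standardized mean follows a t distribution on n-1 degrees of freedom. The 1.96 interval is then too narrow, most of all where there are fewest data.

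In this study the smallest cells are likely to be at Week 130. SAP 3.1 gives "Treatment period: up to approximately 32 months", but it also anticipates that the time from first entry until "trofinetide receives marketing authorization and is marketed will be 29 months", and gives as an example that someone entering "6 months after the first subject enters, will receive treatment with trofinetide for approximately 23 months". Late entrants would therefore never reach the Week 130 window, and the longest follow-up would carry the intervals that are furthest from their label. What is at stake is whether that label is accurate; no test or decision rests on it.

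**Working it through.** **Planned size.** SAP 3.4: 180 × 0.85 = 153, which reproduces the stated figure. The documents give no split by antecedent group; an equal split (assumed) gives 153 / 2 = 76.5, taken as 76.

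**Coverage for normal changes.** With T the t distribution function, coverage = 2·T(1.96; n-1) - 1. The relative width of the correct interval is t(0.975, n-1) / 1.96.

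| n | Coverage of mean ± 1.96·SE | Shortfall (percentage points) | t quantile | Width ratio |
|---|---|---|---|---|
| 153 | 94.8% | 0.2 | 1.976 | 1.008 |
| 76 | 94.6% | 0.4 | 1.992 | 1.016 |
| 26 | 93.9% | 1.1 | 2.060 | 1.051 |
| 13 | 92.6% | 2.4 | 2.179 | 1.112 |
| 10 | 91.8% | 3.2 | 2.262 | 1.154 |
| 5 | 87.8% | 7.2 | 2.776 | 1.417 |

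A simulation of 400,000 normal samples per size agreed: 94.8% at 153, 94.7% at 76 and 91.8% at 10.

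**How small Week 130 cells could be.** The Week 130 window opens on day 820 (SAP Table 2). SAP 5.5.1 places early-termination assessments by study day, so a subject stopped before day 820 adds nothing to Week 130. If the study stops S months after first entry, only subjects who enter within (S × 30.4375 - 820) / 30.4375 months reach the window:

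- S = 29 (SAP 3.1): (882.7 - 820) / 30.4375 = 2.06 months
- S = 30 (Protocol 1.4): (913.1 - 820) / 30.4375 = 3.06 months
- S = 32 (SAP 3.1): (974.0 - 820) / 30.4375 = 5.06 months

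Assume uniform entry over E months, two equal groups, dropout d of 0 to 20%, and n rounded down. Then n per group = 153 × min(1, months / E) × (1 - d) / 2. For example, S = 29, E = 6, d = 0 gives 153 × 2.06 / 6 / 2 = 26.3, so 26.

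| Accrual (assumed) | Stop at 29 months | Stop at 30 months | Stop at 32 months |
|---|---|---|---|
| 6 months | n 21–26, 93.6–93.9% | n 31–39, 94.1–94.3% | n 51–64, 94.4–94.6% |
| 12 months | n 10–13, 91.8–92.6% | n 15–19, 93.0–93.4% | n 25–32, 93.8–94.1% |

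Only the extreme corner of 24-month accrual with a 29-month stop reaches n = 5–6 (87.8–89.3%).

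**Ordinal ratings.** Here the normal formula is only a guide. Exact enumeration for a change of -1, 0 or +1, with assumed probabilities, gives this coverage (1.96, then t):

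| Probabilities of -1 / 0 / +1 | n = 5 | n = 10 | n = 13 | n = 26 | n = 76 |
|---|---|---|---|---|---|
| 0.1 / 0.8 / 0.1 | 98.6, 99.9 | 93.7, 98.7 | 97.5, 97.6 | 93.7, 95.1 | 94.6, 95.2 |
| 0.3 / 0.65 / 0.05 | 80.3, 88.1 | 93.3, 96.3 | 89.4, 92.3 | 93.7, 94.4 | 94.6, 94.9 |

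Under stronger skew (0.15 / 0.83 / 0.02) the figures are 79.4 and 80.2 at n = 10, and 91.0 and 91.1 at n = 26. In the first row all changes are equal, so the interval has zero width, in 32.8% of samples at n = 5 and 10.7% at n = 10. Those intervals sit at the true value of zero and inflate the coverage shown.

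**The case against.** The strongest reply is that the edit is nearly invisible at the only size the documents plan. SAP 5.1 prints limits to one more decimal than the raw data, so 0.1 for these integer scores. Assuming an RSBQ change SD of 5 to 15, the change of multiplier moves each limit by about 0.006–0.019 at n = 153 and 0.018–0.055 at n = 76. It reaches about 0.1–0.3 at n = 26. This stands.

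The small Week 130 cells are also constructed. The six-month lag in SAP 3.1 describes one example entrant, not an accrual period, and the 12- and 24-month cases have no textual basis. With a 32-month stop and six-month accrual, the shortfall is only 0.4–0.6 points. This stands as a limit on the size of the point. SAP 3.1 does say that not everyone will be treated for the full period, so some shrinkage is expected.

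The t quantile is not a sure gain for the six ordinal ratings. In the symmetric example it lies further from 95% than 1.96 does at n = 5, 10 and 13, and under strong skew it barely helps. This also stands: the clear gain is for the three sum scores, provided their changes are near normal, which the documents do not show.

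Finally, nothing is tested, the formula is disclosed, and n, SD and SE are tabulated, so a reader can form the t interval. That settles the priority as low, but the stated multiplier still does not match its label.

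**Conclusion.** The point holds and is minor. For approximately normal changes, the SAP 5.1 interval covers less than 95% at every cell size. The shortfall is negligible in full groups: 0.2 percentage points of coverage at 153 and 0.4 at an assumed 76 per group. With six-month accrual and a 29- or 30-month stop it would be 0.7–1.4 points per group at Week 130, and with 12-month accrual 1.6–3.2 points. These Week 130 figures rest on assumed accrual, an equal split and 0–20% dropout. For the six ordinal ratings the direction of the error is not fixed. No study decision changes. Nor does the point touch a separate limitation, that small Week 130 cells would hold only early entrants still on treatment.

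**What to change.** In SAP 5.1, replace 1.96 with t(0.975, n-1), where n is the number of non-missing changes in that cell. Protocol 9.5.1 specifies no confidence interval, so the protocol need not change.

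The cost is one phrase in the SAP and wider intervals: 0.8% at n = 153, 1.6% at 76, 5% at 26, 11% at 13 and 15% at 10. No estimate changes and no new data are needed.

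A short table note should say that the interval is approximate for the ordinal ratings. The change does not repair strong skew or cells in which all changes are equal.
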